9.4 OTHER SECONDARY EFFICACY MEASURES

9.4.1 St. George's Respiratory Questionnaire

The SGRQ is a 50-item questionnaire designed to measure impact on overall health, daily life, and perceived wellbeing in patients with obstructive airways disease (Jones 1992). Scores for the SGRQ are totaled into 3 components (symptoms, activities, impacts) as well as a total score. Scores weighted and expressed as a range from 0 to 100, with higher scores indicating more limitations. The current established minimal important difference for SGRQ scores in an average COPD population is -4 units (Jorrit 2015). Calculation of component and total scores are described in the manual (Jones 2009).

Descriptive statistics for the raw and change from baseline to Week 12 values for the SGRQ the components and the total score will be presented for each scheduled visit by treatment.

Additionally, boxplots presenting the raw values and changes from baseline for each visit will be presented. The SGRQ scores will be treated as a continuous variable.

A longitudinal mixed model will be used to describe the change from baseline for the each of the scores over time. All subjects, including those who did not complete both treatment sequences, will be included in the model. A contrast will be calculated for Week 12 to compare the treatment groups with respect to change. The outcome variable will be change from baseline. Independent variables will be treatment, the subject's baseline average SGRQ score, treatment sequence, visit number, and the interaction of visit and treatment.

Observed values for the FAS and PPROT will be used with no imputation for missing values.

9.4.2 University of California San Diego Shortness of Breath Questionnaire

The UCSD SOBQ is a self-administered rating of dyspnea associated with activities of daily living (Eakin 1998). The questionnaire contains 24 items on a 6-point scale, where 0 = "not at all" and 5 = "maximal or unable to do because of breathlessness" and total score are summed across items for a range from 0 to 120. The current established minimal important difference for UCSD SOBQ scores in a chronic lung disease population is 5 units (Ries 2005). Descriptive statistics of the raw and change from baseline to Week 12 values for the UCSD SOBQ score will be presented for each scheduled visit by treatment.

A longitudinal mixed model will be used to describe the change from baseline in the total score over time. All subjects, including those who did not complete both treatment sequences, will be included in the model. A contrast will be calculated for Week 12 to compare the treatment groups with respect to change. The outcome variable will be change from baseline. Independent variables will be treatment, the subject's baseline average UCSD SOBQ score, treatment sequence, visit number, and the interaction of visit and treatment.

Observed values for the FAS and PPROT will be used with no imputation for missing values.

9.4.3

[REDACTED]

[REDACTED]

[REDACTED]

[REDACTED]

9.4.4 Patient Global Assessment

The PGA is a being used to rate subject fatigue and shortness of breath. Subjects will use the Sponsor-provided smart device for at-home capture of the PGA data at or just prior to each study visit. Subjects will be asked to perform the PGA at the same time as the at-home spirometry assessment at all applicable visits. Scores for each are on a 5-point response scale of: “never,” “rarely,” “sometimes,” “often,” or “always” with higher scores indicating a worse symptom rating.

Descriptive statistics for the raw and change from baseline values for the PGA ratings will be presented for each scheduled visit by treatment. Additionally, boxplots presenting the raw values and changes from baseline for each visit may be presented.

Exploratory analyses may be conducted for PGA items to examine floor and ceiling effects, reliability across repeated baseline assessments, and within subgroups to further understand the psychometric properties of PGA measurements.

9.5 EXPLORATORY EFFICACY MEASURES

Exploratory analyses will not be addressed in this SAP. Relevant analyses conducted will be presented in the CSR.

10 SAFETY ANALYSES

The safety of inhaled treprostinil compared to placebo will be evaluated on the following parameters: AEs, vital sign measurements, ECGs, clinical laboratory assessments, PFTs, spirometry, and oxygenation. All safety analyses will be based on the Safety Population (see Section 6). No formal inferential testing will be reported for routine safety analyses.

10.1 EXTENT OF EXPOSURE

Exposure to treprostinil and placebo will be calculated as the date of last dose minus the date of first dose plus 1. If the date of last dose of study drug was missing or unknown, the return date of study drug will be used as an imputed date. All analyses will be presented by treatment and period. These analyses include:

- Duration of exposure (in weeks) to each treatment
- Number of subjects exposed by time (weekly from Baseline Visit respective to treatment)
- Maintenance dose (in mcg QID) during the study (dose subject is maintained on after titration period [ie, the mode of the dose during that treatment period]).

10.2 ADVERSE EVENTS

Adverse events are recorded starting from the time each subject signs the ICF until the time a screen failure is documented, study completion, or early termination. All events recorded by the Investigators will be assigned a MedDRA PT and SOC. The most recently available MedDRA version before the database lock date will be used to assign preferred terms and system organ classes. All presentations will present data by treatment received at the time of the event.

Adverse events that occur during the Washout Period following Treatment Period 1 will be presented as having occurred on the treatment taken by the subject during Treatment Period 1. Similarly, AEs that occur during post-discontinuation follow-up will be presented as having occurred on the treatment taken by the subject during Treatment Period 2. Finally, AE tabulations will allow occurrences during low dose run-in and blinded treatment to be assessed (eg, low dose treprostinil, treprostinil treated, any treprostinil, placebo treated). Non-treatment emergent AEs observed outside of any study drug exposure will not be presented.

In addition, a limited number of presentations may be tabulated for AE data by both treatments received at the time of the event and treatment sequence, including the total rates by sequence.

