#### 3.6 ESTIMATED STUDY DURATION

In the **Original Crossover Design**, subjects will undergo 26 weeks of treatment (over a 34-week period) as follows: at least 2 weeks of low dose (3 breaths QID) inhaled treprostinil treatment during the Screening Period (a minimum of 14 days and a maximum of 18 days if needed to

facilitate scheduling); and 24 weeks on either active or placebo, as per randomization, during Treatment Periods 1 and 2. There will be 2 Washout Periods (no treatment) for a minimum of 7 days (maximum of 14 days). Washout Period 1 (Study Week -1) will occur after the Screening Period and Washout Period 2 (Study Week 13) will occur after Treatment Period 1.

If applicable, subjects will undergo 14 weeks of treatment (over a 21-week period) in the **Contingent Parallel Design** as follows: at least 2 weeks of low dose (3 breaths QID) inhaled treprostinil treatment during the Screening Period (a minimum of 14 days and a maximum of 18 days if needed to facilitate scheduling), a Washout Period (no treatment) for a minimum of 7 days (maximum 14 days), and 12 weeks on either active or placebo, as per randomization.

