# 10.3.4 Safety Analyses

The safety of inhaled treprostinil compared to placebo will be evaluated on the following parameters: AEs, clinical laboratory assessments, ECGs, PE findings, oxygenation, PFTs, vital sign measurements, and at-home spirometry.

All AEs as recorded by the Investigators will be assigned a Medical Dictionary for Regulatory Activities (MedDRA) Preferred Term and System Organ Class by the Sponsor for reporting purposes. The summary of AEs will include the number and percentage of subjects, as well as the number of events reported for each Preferred Term. No inferential analyses are planned for the AEs.

Data collected prior to dosing will serve as baseline values for the evaluation of data collected during the Treatment Period. Summary statistics will be calculated for measured values and changes from baseline values. Treatment-emergent changes in clinical laboratory evaluations, ECGs, oxygenation, PFTs, at-home spirometry, and vital sign measurements will be summarized by treatment group. No inferential analyses are planned on these safety endpoints.

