3 STUDY DESIGN

3.1 GENERAL DESCRIPTION

This is a multicenter, randomized, double-blind, placebo-controlled, 34-week, crossover study of inhaled treprostinil (Tyvaso[®] [treprostinil] Inhalation Solution) in males and females 18 years or older diagnosed with WHO Group 3 pulmonary hypertension (PH) associated with chronic obstructive pulmonary disease (COPD). Subject eligibility will be based on the inclusion and exclusion criteria described in Section 4 of the protocol.

Approximately 136 eligible subjects will be randomized with half of the subjects receiving 12 weeks of active study drug (Period 1) then 12 weeks of placebo (Period 2) and the other half receiving 12 weeks of placebo (Period 1) then 12 weeks of active study drug (Period 2). Under the original study design, all randomized subjects will be treated with both active study drug and placebo.

The study will consist of the following periods:

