10.2.5 Summary of Treatment Emergent Adverse Events

An overall summary of AEs by treatment received at the time of the event and treatment will contain the following:

- Total number of AEs, total number of subjects with at least one AE
- Total number of related AEs, total number of subjects with at least one related AE
- Total number of serious adverse events (SAEs), total number of subjects with at least one SAE
- Total number of AEs leading to study withdrawal
- Total number of AEs leading to treatment discontinuation.

Table summaries of all AEs will present numbers and percentages by SOC and PT of the following by treatment received at the time of the event:

- Subjects with at least one AE
- Subjects with at least one treatment-related AE
- Subjects with at least one SAE
- Subjects with an AE leading to treatment discontinuation.

AEs will also be summarized by treatment received at the time of the event for the following:

- AEs by severity
- AEs by relationship to treatment
- AEs by action taken with treatment, separately
- Listing of all SAEs.

Finally, a table summarizing the AEs that occurred during the pre-randomization run-in phase will be presented for all screened subjects.

Adverse events will be presented in alphabetical order of SOC and by decreasing order of incidence of the PTs.

For these summaries, a subject having the same AE multiple times will only be counted once for the corresponding PT. Similarly, a subject who experienced multiple AEs within the same SOC will be counted only once for that SOC.

A subject experiencing the same AE multiple times or at multiple severities will only be counted once under that PT at the worst severity rating. Similarly, a subject who experiences the same AE multiple times or at multiple severities across multiple PTs within the same SOC will only be counted once for the worst severity rating within the SOC.

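### Adverse event percentages for the run-in and any-treprostinil groupings cover unequal planned windows and have no time denominator

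*SAP*

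**What the plan says.** SAP 10.2 gives examples of how adverse events will be grouped: "AE tabulations will allow occurrences during low dose run-in and blinded treatment to be assessed (eg, low dose treprostinil, treprostinil treated, any treprostinil, placebo treated".

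SAP 10.2.5 sets the summary measure: "Table summaries of all AEs will present numbers and percentages by SOC and PT", split by whichever treatment the subject was on when the event occurred. It also lists overall totals of events. Protocol 10.3.4 agrees: "The summary of AEs will include the number and percentage of subjects, as well as the number of events reported for each Preferred Term". Neither section gives a time denominator in the readable text.

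The windows come from the design. Protocol 3.6 plans "at least 2 weeks of low dose (3 breaths QID) inhaled treprostinil treatment during the Screening Period", with a range of 14 to 18 days. SAP 3.1 describes the blinded part as "half of the subjects receiving 12 weeks of active study drug (Period 1) then 12 weeks of placebo (Period 2"), and the other half in the reverse order.

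SAP 10.1 tabulates duration of exposure by treatment and period, without linking it to adverse events. SAP 10.2 charges events in the washout after Period 1 to the Period 1 treatment. It also allows optional rates by sequence, which it does not define.

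For the contingent parallel design, SAP 12.4.7 replaces the text of 10.2 without repeating the sentence on groupings. SAP 12.4 says that text needing no change is not repeated. SAP 10.2.5 has no replacement.

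**The concern.** A crude percentage of subjects with at least one event rises with the time observed. If columns cover different numbers of weeks, their percentages differ even when the drug does nothing. No formal safety testing is planned (SAP 10; Protocol 10.3.4), so the displayed percentages carry the interpretation.

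Two columns are exposed to this. The run-in column covers about one sixth of the time of the blinded columns. In the crossover, the any-treprostinil column is the run-in plus the blinded treprostinil period, so on a common denominator it can never read lower than blinded treprostinil, whatever the hazard shape. What is at stake is a descriptive safety table that shows an excess or a deficit produced by observation time alone.

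**Working it through.** **1. The plan's own totals.** Protocol 3.6 says that in the crossover "subjects will undergo 26 weeks of treatment (over a 34-week period"), and in the parallel design "subjects will undergo 14 weeks of treatment (over a 21-week period"). These reproduce: 2 + 12 + 12 = 26 and 2 + 12 = 14.

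**2. Planned window per column, crossover.**
- Low dose run-in: 14/7 = 2.0 to 18/7 = 2.6 weeks
- Treprostinil: 12 weeks
- Any treprostinil: 2.0 + 12 = 14.0 to 2.6 + 12 = 14.6 weeks
- Placebo: 12 weeks

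The 7 to 14 days of Washout 2 are added to whichever treatment came first. With balanced sequences and equal retention this adds 0.5 to 1 week on average to both blinded columns (12.5 to 13 weeks each), so it does not separate them.

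**3. Effect of window length alone.** Assumptions, not in the documents: constant hazard, no drug effect, the same 12-week incidence p in every condition, with p from 10% to 50%. Expected percentage at w weeks: f(w) = 1 − (1 − p)^(w/12). For the parallel design, assume that the groupings carry over and allocation is 1:1. Half of the any-treprostinil column then has 14 weeks, and the placebo half has the 2-week run-in only: 0.5·f(14) + 0.5·f(2).

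| p (12 weeks) | Run-in, 2 wk | Treprostinil, 12 wk | Any treprostinil, 14 wk (crossover) | Placebo, 12 wk | Any treprostinil (parallel mix) |
|---|---|---|---|---|---|
| 10% | 1.7% | 10.0% | 11.6% | 10.0% | 6.7% |
| 30% | 5.8% | 30.0% | 34.0% | 30.0% | 19.9% |
| 50% | 10.9% | 50.0% | 55.5% | 50.0% | 33.2% |

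Any treprostinil minus placebo is +1.6, +4.0 and +5.5 points in the crossover, and −3.3, −10.1 and −16.8 points in the parallel mix. With an 18-day run-in the crossover column reads 12.0%, 35.2% and 56.9%, that is +2.0, +5.2 and +6.9 points.

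**4. Subjects with run-in only, crossover.** If a share q of the any-treprostinil denominator has the run-in only, the excess over placebo vanishes at q = [f(14) − f(12)] / [f(14) − f(2)]. At p = 30%: (0.340 − 0.300) / (0.340 − 0.058) = 14%. At 10% and 50% it is 16% and 12%. The crossover excess in step 3 is therefore an upper figure for a given run-in length.

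**5. After adjustment.** Under the same assumptions the rate of first events is −ln(1 − p)/12 in every column and in both designs: 0.88, 2.97 and 5.78 per 100 subject-weeks at p = 10%, 30% and 50%.

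**6. If events cluster at each start.** Let the hazard be 3h in the first 2 weeks of each start and h afterwards, still with no drug effect. Average weekly hazards are:
- run-in: 6h/2 = 3h
- placebo: (6h + 10h)/12 = 1.33h
- any treprostinil, crossover: (6h + 16h)/14 = 1.57h
- any treprostinil, parallel mix: (22h + 6h)/(14 + 2) = 1.75h

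Relative to placebo these are 2.25, 1.18 and 1.31. Rates then overstate the short run-in column and, to a lesser degree, any treprostinil.

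**The case against.** The SAP does not commit to comparing these columns. It introduces them as examples, for description, and states the safety aim as treprostinil compared with placebo. That contrast has equal planned windows of 12 weeks. All of this stands. A reader might infer that the whole adverse event comparison is distorted, and the documents do not support that.

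The summaries are not limited to percentages. Event totals appear in SAP 10.2.5 and Protocol 10.3.4, and exposure in SAP 10.1, so a reader could adjust roughly. This stands in part. Event totals do not give first events, the exposure table is not tied to time at risk, and the readable text does not say whether it covers the run-in.

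The any-treprostinil excess assumes that every subject contributes both the run-in and 12 blinded weeks. Placebo-first subjects who leave before Period 2 do not. Protocol 10.3 defines the Safety Population as enrolled subjects with at least one dose of study drug, and the protocol also calls the run-in drug study drug, so run-in failures may count as well. Step 4 shows how this shrinks the excess.

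Rates would not make the low-dose column comparable. The run-in is first exposure, open label and at a fixed low dose, and intolerant subjects are removed before randomization. Its separate table in SAP 10.2.5 uses all screened subjects. This stands and limits the fix.

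The list of tables named in the SAP's contents is not in the text available, so the lack of an adjusted rate is judged on the readable sections only.

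**Conclusion.** The point holds for the run-in and any-treprostinil columns only. With constant hazard, no drug effect, an assumed 12-week incidence of 10% to 50% and a 14-day run-in, any treprostinil reads up to 1.6 to 5.5 points above placebo in the crossover, and the run-in about 8 to 39 points below placebo. If the groupings carry over to the parallel design, any treprostinil reads below placebo, at about 20% against 30% in the 30% case. SAP 12.4 makes that carry-over plausible, but the text does not settle it.

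Two stronger readings are not supported. A reader might infer that any treprostinil will always look worse than placebo; the direction depends on the design and on how many subjects have the run-in only. A reader might also infer that the SAP plans a low-dose against target-dose comparison; no such comparison appears in the readable text.

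The matter affects descriptive safety reporting. It does not touch efficacy or any formal test.

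**What to change.** In SAP 10.2.5, and by a matching entry in 12.4.7:

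- Show for each adverse event column the number of subjects and the subject-weeks at risk, counted by the same washout attribution rule as the events in SAP 10.2.
- Beside the crude percentages, add the exposure-adjusted incidence rate: subjects with an event divided by subject-weeks to first event or end of the window, per 100 subject-weeks.
- Base any comparison of any treprostinil with placebo on those rates. Crude percentages can stay for blinded treprostinil against placebo.
- State that the low-dose column is descriptive only and is not to be read as a dose response from either percentages or rates, because dose, open-label first exposure, selection and event timing also differ.
- State in 12.4.7 whether the groupings apply in the parallel design and, if so, that placebo-arm subjects enter any treprostinil through the run-in only.

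Dosing dates and event onset dates are already collected, so no new data are needed. The cost is SAP wording and one extra table. The rates assume a roughly constant hazard; step 6 shows the error that remains if events cluster at the start of dosing, and the table should carry that caution.

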10.2.1 Severity of Adverse Event

The severity of AEs will be reported by the Investigator as ‘Mild,’ ‘Moderate,’ or ‘Severe.’

10.2.2 Relationship to Study Treatment

The relationship of the event to the study drug is classified by the Investigator as ‘Not Related,’ ‘Possible,’ or ‘Probable.’ For analytic purposes, AEs classified as ‘Probable’ or ‘Possible’ will be considered ‘Related.’

10.2.3 Action Taken with Study Treatment

For each AE, the Investigator classifies the action taken with the study treatment as 1 of the following: ‘Dose Not Changed,’ ‘Dose Increased,’ ‘Dose Decreased,’ ‘Drug Interrupted,’ ‘Drug Withdrawn,’ ‘Unknown,’ or ‘Not Applicable.’

10.2.4 Outcome of Treatment Emergent Adverse Event

The Investigator categorizes the outcome of each AE as 1 of the following: ‘Fatal,’ ‘Not Recovered/Not Resolved,’ ‘Recovered/Resolved,’ ‘Recovered/Resolved with Sequelae,’ ‘Recovering/Resolving,’ or ‘Unknown.’

10.2.5 Summary of Treatment Emergent Adverse Events

An overall summary of AEs by treatment received at the time of the event and treatment will contain the following:

- Total number of AEs, total number of subjects with at least one AE
- Total number of related AEs, total number of subjects with at least one related AE
- Total number of serious adverse events (SAEs), total number of subjects with at least one SAE
- Total number of AEs leading to study withdrawal
- Total number of AEs leading to treatment discontinuation.

Table summaries of all AEs will present numbers and percentages by SOC and PT of the following by treatment received at the time of the event:

- Subjects with at least one AE
- Subjects with at least one treatment-related AE
- Subjects with at least one SAE
- Subjects with an AE leading to treatment discontinuation.

AEs will also be summarized by treatment received at the time of the event for the following:

- AEs by severity
- AEs by relationship to treatment
- AEs by action taken with treatment, separately
- Listing of all SAEs.

Finally, a table summarizing the AEs that occurred during the pre-randomization run-in phase will be presented for all screened subjects.

Adverse events will be presented in alphabetical order of SOC and by decreasing order of incidence of the PTs.

For these summaries, a subject having the same AE multiple times will only be counted once for the corresponding PT. Similarly, a subject who experienced multiple AEs within the same SOC will be counted only once for that SOC.

A subject experiencing the same AE multiple times or at multiple severities will only be counted once under that PT at the worst severity rating. Similarly, a subject who experiences the same AE multiple times or at multiple severities across multiple PTs within the same SOC will only be counted once for the worst severity rating within the SOC.

